2.6 Verification of hospital discharge date

Study staff will determine when study participants are discharged from the hospital in order to plan and schedule data collection follow-up to ascertain outcomes and to schedule the Home Link intervention home visits (for those in the Home Link arm).

2.7 Post-discharge follow-up

The primary outcome is mortality six months after hospital discharge. Secondary outcomes include mortality 12 months after hospital discharge, number of nights spent in a hospital,

number of ambulatory clinical encounters after the index hospitalization, and patient out-of-pocket costs for medical care. Outcomes will be assessed through scheduled contact and completion of a structured questionnaire with the participant or designated next of kin (either telephonic or in person if telephonic fails) at 8, 12, 26, and 52 weeks. Mortality will be further ascertained through a 26 and 52 week review of the Tshepong Hospital file (including the affiliated Klerksdorp hospital files) and matching of participant national identification numbers to the vital statistics register through consultation with the Department of Home Affairs. Repeat hospitalization will be ascertained using self-report / next of kin report and hospital records. Most subsequent hospitalizations can be expected to be at Tshepong Hospital due to the substantial distance to reach the next nearest hospital (>50 km to a lower level facility). In our prior experience we have observed rare use of alternative hospitals. Clinic visit data will be ascertained by self-report followed by verification through review of clinic paper or electronic (tier.net) records and National Health Laboratory Service electronic records (TrackCare).

Table 2. Scheduled visit windows

Visit name	Period	Primary goal
8 week follow-up	20 – 70 days	Maintain contact with participant
12 week follow-up	71-150 days	Assess care engagement, care satisfaction, mortality
26 week follow-up	151 – 245 days	Assess care engagement, , mortality; conduct psychosocial assessment
26 week hospital file review	>26 weeks post-hospital	Abstract care visits, re-admission, death
26 week Home Affairs vital status review	>26 weeks post-hospital	Match South African ID numbers
26 week care verification	>26 week post-hospital	Use electronic and paper files to verify self-reported clinic visits
52 week follow-up	365-455 days	Assess care engagement, mortality
52 week hospital file review	>365 days post-hospital	Abstract care visits, re-admission, death
52 week Home Affairs vital status review	>365 days post-hospital	Match South African ID numbers

2.7.1 Care verification

Clinical records will be accessed to determine linkage to care status, timing of linkage to care, ART continuation, retention in care, and relevant laboratory results. This will be done through reviewing paper clinic charts, electronic clinic data (tier.net), and electronic laboratory data (NHLs Trackcare system). Linkage between participants and records will be based on matching surname, first name, date of birth, sex, and appropriate date range.

2.7.2 Mortality

Mortality will be ascertained via:

- (1) Telephonic contact with participant (alive) or next of kin, as provided by the participant, reporting a death
- (2) Review of the Tshepong Hospital paper file
- (3) South African Home Affairs vital statistics query using the participant national ID number

Mortality will be assessed after six months and again after twelve months.

2.7.3 Effectiveness of Home Link

Table 3. Effectiveness outcomes

Primary outcome	Mortality at six months by arm	Test of proportions (chi-square)
Secondary outcomes	Mortality at 12 months	Test of proportions (chi-square)
	Time to any non-acute follow-up	Cox proportional hazards
	Number of outpatient follow-up care encounters	Test of medians (Wilcoxon rank sum)
	Number of nights in hospital post-initial discharge	Test of medians (Wilcoxon rank sum)
	Self-reported cost of care	Test of medians (Wilcoxon rank sum)
Process outcomes	Acceptability of intervention	
	Feasibility of intervention	
	Feasibility of clinical trial	

2.7.4 Acceptability & Feasibility

2.7.4.1 Feasibility of Home Link

The goal of this assessment is to evaluate the feasibility of implementing the Home Link intervention and of endpoint ascertainment for the clinical trial of Home Link implementation.

Specific feasibility considerations are:

- 1) The proportion of participants in the Home Link arm who receive each scheduled/expected Home Link home visits
- 2) Success of the study team to ascertain six month mortality

We will assess the trial feasibility based on the proportion of eligible individuals who enroll and the proportion of participants that we are able to collect full outcome data on. We will assess the feasibility of implementing the intervention on the following measures: the proportion of planned home visits that are completed, the proportion of home medical assessments completed, the proportion of home medication reconciliation completed, the proportion of participants who receive patient-centered counseling, and the proportion of participants with identified food insecurity who receive food supplementation/parcels at the first home visit. The proportions will be considered individually and with a composite score to be interpreted in the context of the efficacy results with a general threshold that substantially more than half of components expected to be completed need to be completed for the intervention to be considered feasible.

Success will be based on *a priori* targets of $\geq 90\%$ of planned home visits completed, successful follow-up of $\geq 75\%$ of participants, and vital status ascertainment of $>90\%$ of participants.

Table 4. Feasibility Indicators

Numerator	Denominator	Measure
-----------	-------------	---------

Number with first Home Link visit	Total in Home Link arm	Proportion
Number of completed Home Link visits	Number of planned/attempted Home Link visits	Proportion
Number of home medical assessments completed	Number of planned/attempted/completed Home Link visits	Proportion
Number of home medication reconciliation completed	Number of planned/attempted/completed Home Link visits	Proportion
Number of patient-centered counseling sessions completed	Number of planned/attempted/completed Home Link visits	Proportion
Number of participants who received food parcels	Number of Home Link participants with identified food insecurity pre-discharge	Proportion
Number of participants with 6 month vital status ascertainment	All study participants	Proportion
Number of participants with 6 month care engagement ascertainment For PWH: ≥ 1 HIV care visit For HIV-negative participants: ≥ 1 outpatient clinic visit	All study participants	Proportion
Number of participants with baseline laboratory and medical assessment completed	All study participants	Proportion

Acceptability

Acceptability will be assessed among participants in the intervention arm and health staff using an acceptability questionnaire and in-depth interviews. The (CRF F004) questionnaire based on the theoretical framework of acceptability developed by Sekhon et al. ⁴¹ that has seven core constructs: attitude (how an individual feels about the intervention with confidentiality and receipt of care and medical procedures such as phlebotomy occurring at home), burden (effort required for the intervention), ethics (concurrence with value system), coherence (how well the intervention is understood), opportunity costs, perceived effectiveness, and self-efficacy (confidence in performing or participating in the intervention). The acceptability scores will be interpreted in the context of the study efficacy results with a general threshold of the majority of participants scoring the constructs as acceptable (responses on Likert scale). Findings from the acceptability questionnaire will be further explored through in-depth interviews in a sequential explanatory mixed methods approach (described as follows).

Patient in-depth interviews: We will interview up to 40 patients recruited through a purposive sampling strategy to obtain a maximum variation sample by number of Home Link visits received and HIV status, timing of HIV diagnosis (during index hospitalization or prior, for those living with HIV), hospital readmission, sex, and age group. In-depth interviews will be conducted by trained research assistants in the participant's preferred language. Interviews will explore items identified in the quantitative survey for further exploration and: i) perceptions of and experiences with Home Link including participants perceptions of alignment of services with

needs (framed with the Andersen Behavioral Model), ii) confidentiality, impact of COVID-19 or other concerns with home visits, and iii) perceptions of quality of Home Link care.

Health care worker interviews: We will interview up to 10 health care workers (Home Link team) to understand their perspectives and experiences with delivering the intervention and to explore ways in which the model could be strengthened. We will also assess the perceived impact of COVID-19 on the homebased intervention. All audio-recorded interviews will be transcribed and translated into English (as necessary). Transcripts will be uploaded into qualitative coding software (e.g. Atlas.ti, MaxQDA) for the purposes of coding and analysis. Health care workers will be invited to participate by letter. Further study information and informed consent will be provided in private. The interviews will occur in a private space at a scheduled time convenient to the health care worker.

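### Do the two marks for home-visit completion, and Table 4's mixed denominators, leave the feasibility result undefined?

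*Combined protocol and SAP*

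**What the plan says.** Section 2.7.4.1 opens with two considerations. The first is "The proportion of participants in the Home Link arm who receive each scheduled/expected Home Link home visits"; the second is success in establishing six-month mortality.

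It then lists five delivery measures: visits, medical assessments, medication reconciliation, counselling and food parcels. These are to be looked at one by one and in a composite, "to be interpreted in the context of the efficacy results" and "with a general threshold that substantially more than half of components expected to be completed need to be completed" if the intervention is to be called feasible. No number is put on that mark and no formula is given for the composite.

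The following paragraph defines success by targets fixed in advance. The 90% figure is attached to the words "of planned home visits completed, successful follow-up of"; the other two targets are at least 75% followed up and more than 90% with known vital status.

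Table 4 gives numerators and denominators:
- Completed visits are divided by "Number of planned/attempted Home Link visits".
- Assessments, reconciliations and counselling sessions are divided by "Number of planned/attempted/completed Home Link visits".
- The only participant-level visit row is "Number with first Home Link visit", over the whole Home Link arm.

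The text counts counselling by person ("the proportion of participants who receive patient-centered counseling"), while Tables 4, 5 and 7 count sessions. Tables 5 and 7 put visit completion over planned visits and state no threshold.

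**The concern.** Section 3.2 calls feasibility and acceptability the primary goal, and the Study Summary expects the pilot to deliver a protocol ready for a full trial. Visit delivery is the core of the intervention, so its criterion ought to be unambiguous.

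Read quickly, it is not. One measure is judged against two marks, one of them without a number, and a result between them has no named conclusion. If the Table 4 denominator may be planned or attempted visits, the same data could pass or fail the 90% target. The first-listed participant-level measure has a table row only for the first visit. The lower mark is also read alongside the efficacy results, which could invite a generous reading of delivery if mortality looks favourable. At stake would be a pilot that reports its intervention as feasible on a criterion settled after the data were seen.

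**Working it through.** The plan derives no figure for these criteria, so there is nothing to reproduce. The check is how far the result can move, and whether the plan permits the move.

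**Inputs.** The Home Link arm is 30 + 90 = 120 participants (section 2.4.2). Each has up to 6 visits, one week after discharge and then every two weeks (section 2.5.2). The ceiling is 120 × 6 = 720 planned visits. Discharge from home visits, death, withdrawal and late exclusion lower it.

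**Two marks.**
- The target needs 0.90 × 720 = 648 completed visits. A bare majority is 361.
- Anything from 361 to 647 misses the target. At 576 visits, 576/720 = 80%: target missed, while the lower mark can be claimed.
- These statements are compatible. The lower mark concerns the delivery components in general. The success targets combine visit completion with follow-up and vital status, so they also cover trial conduct.

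**Denominator.** If exactly 90% of attempted visits are completed, then completed/planned = 0.90 × (attempted/planned). The attempt shares below are assumed.

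| Attempted / planned | Completed / planned |
|---|---|
| 95% | 85.5% |
| 90% | 81.0% |
| 85% | 76.5% |
| 80% | 72.0% |

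For example, 612 completed visits are 612/680 = 90.0% of 680 attempted but 612/720 = 85.0% of planned.

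Whether the plan allows this choice is settled by comparing the places that define the measure:

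| Place | Denominator | Threshold |
|---|---|---|
| 2.7.4.1, list of measures | planned | general floor |
| 2.7.4.1, success target | planned | at least 90% |
| Table 5 | planned | none |
| Table 7 (analysis section) | planned | none |
| Table 4 | planned/attempted | none |

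The only place with a 90% threshold says planned. The only place that says attempted has no threshold, and its slash can be read as reporting both versions. The gap of 4.5 to 18 percentage points (90 − 85.5 to 90 − 72) therefore measures a departure from the stated target, not a latitude within it.

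**Component rows.** Assessments, reconciliations and counselling carry no 90% target, only the general floor. Suppose 580 assessments in the example above: 580/720 = 80.6% of planned, 580/680 = 85.3% of attempted, 580/612 = 94.8% of completed visits. All are well above half. The versions answer different questions (reach, and content once a visit takes place) and can be shown together.

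**Participant level.** At exactly 90% of 720 visits, 72 are missed. One miss each in 72 people leaves (120 − 72)/120 = 40% with every visit; all misses in 12 people leave (120 − 12)/120 = 90%. With 4 visits due each (assumed), 48 of 480 are missed and the range is (120 − 48)/120 = 60% to 90%. These are extreme allocations, they apply only if the measure means every visit rather than each visit in turn, and no threshold is attached to it. It is already promised in the text and can be reported without a table row.

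**The case for a change.** The strongest case for a change is that delivery is what this pilot is for, and that the word planned is itself undefined. The Study Summary reports 54% readmission and 26% mortality by six months in the prior cohort, and visits stop on discharge from the intervention, so many scheduled visits may never fall due. Table 4 is the only place with formal numerators and denominators, and it is the one that is unclear. Reading feasibility beside efficacy is also awkward when Table 9 gives 80% power only for a fall from 26% to 10%, and about 16% to 67% for the smaller falls listed. The edit would be wording only.

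Part of this stands. The lower mark should have had a number, the composite a formula, and counselling one unit. A report will have to say how visits after death, withdrawal, loss to follow-up or late exclusion were counted. But the material for a sensible rule is in the plan: the schedule in section 2.5.2, the three-month limit in the Study Summary, and the discharge, transition and termination forms in Table 8. Attempted visits are the less secure basis, because Table 10 schedules the Home Link forms at home visits and no listed form is specifically for failed attempts. This favours the reading the target already has.

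Reading feasibility in the light of efficacy is a matter of preference. Section 2.7.4.1 (Acceptability) does the same for the acceptability scores, and the numerical targets are not conditioned on efficacy. Nothing shows that this produces a wrong result.

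**Conclusion.** No change is needed. Followed as written, the plan gives a definite primary reading of visit completion: completed over planned visits, judged against 90%. With the 720-visit ceiling that is 648 visits, and a result of 80% is a missed target whatever is also said about the general floor. The 72.0% to 85.5% equivalents arise only if the target's own denominator is replaced, and they rest on assumed attempt rates.

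The remaining points are missing detail and table tidying: an unnumbered minimum, an unspecified composite, slashed denominators, two counselling units and one measure without a full table row. Table 3 lists feasibility as a process outcome with no test, no progression rule depends on either mark, and the six-month mortality comparison and its power do not move. An analyst can fill the gaps by keeping planned visits primary, stating how they were counted, and showing the other versions as description.

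This conclusion rests on reading the lower mark as a floor and the 90% as a target. The protocol does not say so outright, but it is the natural reading and nothing in the text contradicts it.

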2.7.4.2 Bereaved Family members

Interviews with the bereaved family members: We will interview family members of up to 20 deceased participants to understand their experiences around the time of the passing of the participant, including what care the participant sought, how long they were ill for and what the family members think could have been done to assist the participant. In-depth interviews will be conducted by trained research assistants in the participant's preferred language. All audio-recorded interviews will be transcribed and translated into English (as necessary). Transcripts will be uploaded into qualitative coding software (e.g. Atlas.ti, MaxQDA) for the purposes of coding and analysis. Further study information and informed consent will be provided in private. The interviews will occur in a private space at a scheduled time convenient to the participant.

2.7.4.3 Effect of intervention on barriers to care engagement

We will compare, by study arm, constructs anticipated to be effected by the intervention: care access, burden of treatment including cost to the patient and time spent by the patient, patient satisfaction, correct medication administration, internalized and experienced HIV stigma, social support, and food security (Table 5).

Time spent and patient-level financial cost of care will be ascertained by participant self-report using a field team member administered questionnaire with questions focusing on the last clinical contact (clinic or household visit) since hospital discharge, the total number of contacts (visits), the cost of transport and incidental expenses with going to the clinic and lost wages. Specific cost characteristics (such as transport cost and date of clinical care visit) will be verified using objective measures such as local mini-bus fares and medical file abstraction (at 26 weeks after discharge).

Table 5. Measures and analysis for feasibility, acceptability, and effects on engagement in care

Assessment	Assessment methods	Timing	Statistical test	
			Feasibility and Acceptability	
Trial: Feasibility	Proportion of enrolled participants among approached and eligible patients Proportion of participants with complete follow-up	base-line 1 year	Proportion, total study	

Intervention: Feasibility	Proportion of planned home visits successfully completed, patient-centered counseling sessions completed, medical assessments, medication reconciliations, and food security management	3 m	Proportion, Home Link arm
Acceptability	Acceptability questionnaires with 7 acceptability domains for HCWs and participants	3 m	Proportion, Home Link arm
Acceptability	In depth interviews	3 m	Thematic analysis
Effects on care engagement barriers			
Patient cost	Structured questionnaire for participant self-report	3 m, 6m	Wilcoxon rank sum
Care satisfaction	Adapted South African care satisfaction survey ⁴⁴	3 m	Wilcoxon rank sum test
Medication reconciliation	Reconciling planned meds on discharged actual meds with patient & way that patient is taking	3 m	Proportion, Home Link arm
HIV stigma	Short form HIV stigma scale ^{45,46}	baseline, 6 months	Wilcoxon rank sum test
Social Support	MOS social support instrument ⁴⁷	baseline, 6 months	Wilcoxon rank sum test
Food security	Three question scale	baseline, 6 months	Wilcoxon rank sum test
Depression	CES-D (short)	Baseline, 6 months	Proportion
Alcohol use	Alcohol use disorder identification test (AUDIT), shortened version	Baseline, 6 months	Proportion

Medical conditions and psychosocial needs will be assessed prior to hospital discharge and post-hospital by using Home Link visit and other care contact records.

a. Medical assessment prior to hospital discharge: Clinical data will be abstracted or specifically obtained for the study, if not in the clinical record: HIV viral load, CD4 count, HIV drug resistance testing, Xpert Ultra for rapid TB diagnosis, discharge diagnoses, and discharge medications.

Blood will be drawn from all participants living with HIV for drug resistance testing; however, we will only conduct the drug resistance test if the viral load result is >1000 copies/mL. We may use leftover specimen from the drug resistance test to repeat the viral load and drug resistance test using a plasma separation card in collaboration with the National Institute for Communicable Diseases (NICD).

b. Psychosocial assessment prior to hospital discharge: social support, depression, economic status, and HIV stigma will be measured. The 12-item HIV stigma scale⁴⁵ (including enacted, internalized, and anticipated stigma components), CES-D (short) depression scale, MOS social support instrument, food security, and AUDIT alcohol use instrument will be administered to participants prior to discharge (E002).

c. Post-hospital services delivered: All post-hospital assessments (Home Link visit clinical instrument (HL001), participant challenges identified during patient-centered counseling sessions (from structured counselor notes), triage decisions from the discharge officer, findings on laboratory testing, and clinical evaluation during inpatient or ambulatory care that Home Link arm participants receive will be abstracted from hospital or clinic paper or electronic records and

the electronic National Health Laboratory Service records. These data will be organized to describe the intensity of care, psychosocial needs, clinical decision making, and most common clinical scenarios.

Sampling: All participants will have in-hospital laboratory and psychosocial assessments. All participants in the Home Link arm will be included in the assessment of post-discharge needs and triage outcomes.

2.8 Analysis

2.8.1.1 Effectiveness analysis

Table 6. Effectiveness outcomes

Primary outcome	Mortality at six months by arm	Test of proportions (chi-square)
Secondary outcomes	Mortality at 12 months	Test of proportions (chi-square)
	Time to any non-acute follow-up	Cox proportional hazards
	Number of outpatient follow-up care encounters	Test of medians (Wilcoxon rank sum)
	Number of nights in hospital post-initial discharge	Test of medians (Wilcoxon rank sum)
	Self-reported cost of care	Test of medians (Wilcoxon rank sum)

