2.3 Study Population

The population is comprised of adults (≥ 18 years old), either male or female, spending at least two nights in a medical ward of Tshepong Hospital. We will only include individuals with known HIV status, either HIV-positive or HIV-negative. We propose to recruit up to 180 HIV-positive and 60 HIV-uninfected participants.

Randomization to the intervention vs control arms will be stratified by HIV status.

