2.4.2 Randomization

The total sample size is 180 HIV-positive and 60 HIV-uninfected adults. There will be a total of four study arms comprising of two arms for HIV uninfected and two arms for PWH. We will

perform individual randomization blocked by HIV-status to enroll 30 HIV-uninfected adults per arm and 90 PWH per arm (Figure 2).

[figure not shown]

Figure 2: Randomization Study Arms for Home Link Intervention

1. Randomization of hospital patients for recruitment: On each participant recruiting day, a list of all medical ward patients will be generated, and each patient will then be randomly listed in order of planned recruitment. Patients will be approached at any time after admission if they are next on the list for recruitment until the enrolment target is reached for that day. A new list will be generated each day including only those patients admitted 2 days prior (or on Thursday, Friday and Saturday on Mondays).
2. Randomization to study arm: After informed consent and completion of baseline CRFs the participant will be randomized to care as usual or Home Link arm.

Randomization will be conducted immediately after eligibility criteria for the participant has been documented and informed consent has been signed. Participants will be randomized 1:1 to either the care as usual or the Home Link intervention arms using computer-generated random numbers, stratified by HIV-status.

A study staff member will SMS a dedicated study telephone number – staffed by someone not linked to any other aspect of the conduct of the study. Details of the eligible participant, including randomization group (1=living with HIV; 2=living without HIV), initials (first two letters of the first name and first two letters of the surname), age, and sex, will be sent via SMS to the randomizing team. A member of the randomizing team will then relay the allocation details (within 15 minutes) to the study staff member

who requested the randomization via SMS. Proof of randomization will be sent to the study staff member who will place the proof into the participants' study file.

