3.2 Study sample size justification

We propose to recruit a sample of 240 participants randomized 1:1 into care as usual and Care Link arms. The participants will be blocked to include 30 HIV-uninfected adults and 90 people living with HIV per arm. The sample size has been determined to be feasible given time and budget limitations while still providing insight into the efficacy. Using the base rate of mortality from our preliminary study of 26% and an alpha of 0.05 and a sample size of 120 split 1:1 in care as usual and Home Link arms we have represented power versus intervention arm mortality, with sub-group analysis limited to PWH, in Table 11. We note that the primary goal is feasibility and acceptability. We are appropriately powered only for a substantial decrease in mortality from 26% to 10%.

Table 9. Power by varying effect size on reducing post-hospital mortality

alpha	power	N	N1	N2	delta	p1	p2
.05	.1589	180	90	90	-.06	.26	.2
.05	.2527	180	90	90	-.08	.26	.18
.05	.3764	180	90	90	-.1	.26	.16
.05	.5212	180	90	90	-.12	.26	.14
.05	.6704	180	90	90	-.14	.26	.12
.05	.803	180	90	90	-.16	.26	.1
.05	.9019	180	90	90	-.18	.26	.08

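### Section 3.2 gives 120 as the sample size behind a power table built on 180 PWH, and the primary mortality test (Tables 3 and 6) names no population and ignores the HIV stratum used in randomisation

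*Combined protocol and SAP*

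**What the plan says.** Section 2.3: "Randomization to the intervention vs control arms will be stratified by HIV status". Sections 2.4.2 and 3.2 put 90 PWH and 30 HIV-uninfected adults in each of two 1:1 arms, 240 in all.

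Table 3 (section 2.7.3) and Table 6 (section 2.8.1.1) give the primary outcome as "Mortality at six months by arm" and the method as "Test of proportions (chi-square". Neither names an analysis population or a stratified or adjusted test. The only regression, in section 2.8.1.4, belongs to the needs analysis. Its prespecified covariates are sex, age and arm, not HIV status.

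Section 3.2 computes power from a 26% base rate, alpha 0.05 and "a sample size of 120 split 1:1 in care as usual and Home Link arms", "with sub-group analysis limited to PWH, in Table 11". The table beneath is Table 9, and each of its seven rows has N = 180, 90 per arm. The list of tables ends at Table 10. The section concludes: "We are appropriately powered only for a substantial decrease in mortality from 26% to 10" per cent. It also says: "We note that the primary goal is feasibility and acceptability".

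The 26% comes from 121 discharged PWH in the preliminary study (Study Summary). The documents give no mortality rate for HIV-uninfected participants and no power for all 240.

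**The concern.** Three things do not fit together.

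- The sample size in the power sentence disagrees with the table that it introduces.
- The only power figure belongs to a comparison that section 3.2 calls a sub-group, while the primary-outcome row does not say whether it means PWH or everyone. The study aims, the base rate and Table 9 point to PWH. The sub-group wording and primary objective 1, which has no HIV restriction, point to all 240.
- The design stratifies on HIV status and the primary test ignores it.

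The main stake is the second. With two plausible primary populations and neither named, the choice could be made after mortality by arm is known. The adequate-power statement also does not carry over to an all-participant test.

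**Working it through.** **1. Reproducing Table 9.** Inputs from section 3.2: p1 = 0.26, p2 = 0.10, n = 90 per arm, alpha 0.05. The section does not say one- or two-sided; two-sided reproduces the table, while one-sided would give 0.880.

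Power = Φ((d − 1.96·s0)/s1) + Φ((−d − 1.96·s0)/s1), where d = p1 − p2, s0 = √(2·p̄(1−p̄)/n), s1 = √(p1(1−p1)/n + p2(1−p2)/n) and p̄ = (p1+p2)/2.

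Here d = 0.16 and p̄ = 0.18. Then s0 = √(2 × 0.18 × 0.82/90) = 0.0573 and s1 = √((0.26 × 0.74 + 0.10 × 0.90)/90) = 0.0560. (0.16 − 1.96 × 0.0573)/0.0560 = 0.852, so power = 0.803, as printed. The other six rows (.1589, .2527, .3764, .5212, .6704, .9019) also match to four decimals at 90 per arm.

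**2. Trying the 120.** Same formula, 26% against 10%:

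| Reading of 120 | n per arm | Power |
|---|---|---|
| Total | 60 | 0.629 |
| Per arm | 120 | 0.902 |
| Table 9 (180 in total) | 90 | 0.803 |

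Neither reading gives the printed figure. The sentence is wrong and the table is right.

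**3. Power for all 240.** This needs HIV-uninfected control mortality q, which the documents do not give. I **assume** q = 3, 5, 10, 15 or 20%, and either no effect in that stratum or the PWH risk ratio (0.10/0.26). PWH stay at 26% against 10%, and all 240 are analysed. Control mortality over everyone is 0.75 × 0.26 + 0.25 × q, which is 20.3% to 24.5% rather than 26%.

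Power comes from exact enumeration of all binomial outcomes (90 + 30 per arm), rejecting when the statistic exceeds 3.84. The crude statistic is the pooled chi-square on 120 against 120. The Cochran-Mantel-Haenszel (CMH) statistic, without continuity correction, is [Σ(x1−x2)/2]² / Σ m(N−m)/(4(N−1)). The sums run over the two strata, x1 and x2 are deaths by arm, m is total deaths and N is stratum size.

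| Assumed q | No effect in HIV-uninfected: crude / CMH | Same risk ratio: crude / CMH | Size, no effect anywhere: crude / CMH |
|---|---|---|---|
| 3% | 0.778 / 0.787 | 0.816 / 0.826 | 0.044 / 0.050 |
| 5% | 0.765 / 0.771 | 0.827 / 0.834 | 0.045 / 0.050 |
| 10% | 0.734 / 0.733 | 0.851 / 0.853 | 0.048 / 0.050 |
| 15% | 0.707 / 0.701 | 0.873 / 0.872 | 0.049 / 0.050 |
| 20% | 0.681 / 0.677 | 0.892 / 0.890 | 0.050 / 0.050 |

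Exact power for PWH alone is 0.812. Pooling therefore changes power by between 0.677 − 0.812, about −13 points, and 0.892 − 0.812 = +8 points. With CMH, the break-even HIV-uninfected risk ratio is about 0.61 to 0.65: pooling gains power below it and loses power above it.

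**4. Crude against stratified.** The difference in power runs from about −0.5 point (0.7066 against 0.7015 at q = 15%, no effect) to about +1 point (0.816 against 0.826 at q = 3%, same risk ratio). CMH is slightly lower in 5 of the 10 scenarios. Its benefit is size, which stays at 0.050 while the crude test falls to 0.044 at the lowest assumed rate.

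**The case against.** The strongest reply is that little turns on this. The trial is a pilot whose stated primary goal is feasibility and acceptability. Section 5.5 sets no stopping rule for effectiveness and concedes that the sample may be too small to show a clear difference. That stands, and it sets the weight of the point. Six-month mortality is still the named primary outcome in section 2.7 and in Tables 3 and 6.

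Several stronger readings are tempting, and the documents do not support them:

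- **That the trial has only 63% power, or that Table 9 is wrong.** The table is correct for the 180 PWH to be recruited. The 120 and the Table 11 reference are slips in the text.
- **That the 80% cannot be attributed to any comparison.** The reference to PWH in section 3.2 and the 90-per-arm rows show that it is the PWH comparison. What is missing is whether that comparison is the primary one.
- **That the crude chi-square is invalid.** It is slightly conservative, and its power is almost the same as that of the stratified test.
- **That the four arms counted in section 2.4.2 leave the comparison undefined.** They are two HIV strata times two arms, and the same section then randomises 1:1 between usual care and Home Link.

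It is also fair to say that the 0.68 to 0.89 range rests on chosen rates. Widening the assumed rates widens it: with q from 2% to 26%, a normal approximation gives about 0.64 to 0.90. The range illustrates dependence on an unstated input and should not be copied into the protocol as a finding.

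**Conclusion.** The point holds, with minor importance. Two items in section 3.2 are wrong as written: the 120, which should be the 180 PWH of Table 9, and the table number. Two items are missing from Tables 3 and 6: the primary population, and use of the randomisation stratum if that population is everyone.

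The 26% base rate and the 0.803 apply to PWH only. Power for all 240 cannot be derived from the documents. It is about 0.68 to 0.89 if HIV-uninfected control mortality is 3% to 20%, the effect in that stratum lies between none and the PWH risk ratio, and nobody is lost to the late exclusions of section 2.3.2. The population choice can therefore matter by several points of power in either direction. The choice between crude and stratified tests matters by about one point at most, with crude size of 0.044 to 0.050.

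**What to change.** 1. In section 3.2, change 120 to 180 PWH (90 per arm), change Table 11 to Table 9, and say that the adequate-power statement applies to the PWH comparison.
2. Before mortality is analysed by arm, state in Tables 3 and 6 whether PWH or all 240 is the primary population, and report the other as supporting. If all 240 is primary, the sponsor should state an assumed HIV-uninfected mortality, the effect expected in that stratum, and the resulting power.
3. For any all-participant mortality comparison, replace the crude chi-square with a Cochran-Mantel-Haenszel test stratified by HIV status, and report an HIV-stratified risk difference with its 95% confidence interval.

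The cost is wording in section 3.2 and Tables 3 and 6, plus one power calculation if all 240 is chosen. No new data or participants are needed. The price of item 3 is at most about half a point of power in some of the scenarios above, in exchange for nominal size.
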